### 11.3.3 Wake-Promoting Agents

Randomization is stratified by concomitant use of wake-promoting agents (Yes/No). Medications that are considered wake-promoting agents are:

- Solriamfetol/Sunosi
- Modafinil/Provigil
- Armodafinil/Nuvigil
- Lisdexamfetamine Dimesylate/Vyvanse
- Dexmethylphenidate/Focalin
- Methylphenidate/Adhansia, Aptensio, Concerta, Cotempla, Daytrana, Jornay, Metadate, Methylin, Quillichew, Quillivant, Ritalin
- Amphetamine and Amphetamine Salts/Adderall, Adzenys, Desoxyn, Dexedrine, Dyanavel, Eveko, Mydayis, Procentra, Zenedi

The EDC stratification is based on review of these medications prior to randomization (i.e., to identify patients who were taking wake-promoting agents).

The identification of patients who were on wake-promoting agents at the time of randomization, based on review of the medications collected in EDC, will be done prior to database lock and study unblinding for the Double-Blind Phase.

The medical monitor will review the list of medications prior to unblinding of the study for the Double-Blind Treatment Phase to finalize a list of medications considered wake-promoting agents. The finalized list will be used to determine if the patients were taking wake-promoting agents at the time of randomization.

If the start and/or stop dates are partial/missing, the imputations rules defined in [Appendix 2](#) will be used to determine if the medication was taken at the time of the first dose of study drug. If it is not possible to determine if the medication was taken at the time of the first dose of study drug, it will be assumed that the medication was not concomitant.

Number (%) of patients on a wake-promoting agents will be tabulated and summarized.

### 11.3.4 Extent of Study Drug Exposure

The descriptive statistics will be provided by treatment group for the Double-Blind Treatment Phase analyses and by treatment group received during the Double-Blind Treatment Phase and total for the OLE Phase analyses.

---

#### 11.3.4.1 Double-Blind Treatment Phase

The duration of exposure to study drug, number of days dose is taken and compliance (during the stable dose period) with study drug dosing will be summarized for the Double-Blind safety population. In addition, the number of tablets taken (i.e., returned - dispensed) will be listed for the titration phase and the stable dose phase in the Double-Blind Treatment Phase.

Study drug accountability including bottle number and number of dispensed and returned tablets will be listed. Study drug not returned will be assumed to have been taken.

Percentage of patients meeting study drug compliance during the stable-dose period will be summarized in the following categories: <80%, ≥80% to ≤120%, and >120%. Major non-compliance is defined as compliance <80% or compliance >120%.

**Duration of exposure:** Date of last dose in the Double-Blind Treatment Phase – date of first dose in the Double-Blind Treatment Phase + 1.

**Number of days with at least one dose (tablet) taken:** Duration of exposure in the Double-Blind Treatment Phase – number of days with missed doses in the Double-Blind Treatment Phase.

Study Drug Compliance (stable-dose period): The start date of the stable dose period is the date of Visit 3 (Day 22), and the end of the stable dose period is the last dose date in the Double-Blind Treatment Phase; during that period each patient should take 2 tablets each morning; i.e., compliance is the number of tablets taken during that period (i.e., sum of the tablets dispensed minus the sum of the tablets returned) divided by (2 times the number of days in the period [date of last dose – dispensed date at Visit 3 + 1]).

#### 11.3.4.2 OLE Phase

The duration of exposure to study drug will be summarized for the OLE safety population. Study drug accountability and number of dispensed and returned tablets will be listed.

**Duration of exposure:** Date of last dose in the OLE Phase – date of first dose in the OLE Phase + 1,

In addition, the following measures of changes in planned dose will be summarized for the OLE safety population:

- Planned average daily dose: sum of the daily dose x for the duration of intake divided by the duration (end date minus start date + 1) of exposure;
- Number and percentage of patients with at least one dose adjustment per reason (AE, dosing error, rechallenge, insufficient effectiveness, change in dose assignment criteria and other);
- Number and percentage of patients with one dose adjustment, with 2 dose adjustments and with > 2 dose adjustments due to any reason;
- Number and percentage of patients with one dose adjustment, with 2 dose adjustments and with > 2 dose adjustments due to AE;
- Number and percentage of patients with one dose adjustment, with 2 dose adjustments and with > 2 dose adjustments due to rechallenge;
- Number and percentage of patients with one dose adjustment, with 2 dose adjustments and with > 2 dose adjustments due to insufficient effectiveness.

### 11.4 Efficacy Analyses

For the inferential analysis, the stratification factor of wake-promoting agents (Yes/No) will be based on the stratification factor derived in the EDC. If there is more than 10% difference between the stratification factor recorded in IRT versus the stratification factor derived from the prior and concomitant in the EDC (see section 11.3.3), the primary analysis will be repeated using the stratification factor reported in the IRT.

### 11.4.1 Double-Blind Treatment Phase

All efficacy analyses will be performed on the mITT Population. The analysis approaches for the efficacy endpoints at Visit 5 are detailed in [Table 7](#). Similar analyses (where applicable) for efficacy endpoints collected at Visit 4 will be conducted as well.

**Table 7: Double-Blind Inferential Analyses Strategy**

Endpoint	Primary/ Secondary/ Exploratory	Inference model	Comparisons of interest
CFB in DSS score at Week 11 (Visit 5)	Primary	MMRM	Higher dose vs. Placebo; Lower dose vs. Placebo; Pooled active vs. Placebo
CFB in ESS score at Week 11 (Visit 5)	Secondary	MMRM	Higher dose vs. Placebo; Lower dose vs. Placebo; Pooled active vs. Placebo
CFB in FSS score at Week 11 (Visit 5)	Secondary	MMRM	Higher dose vs. Placebo; Lower dose vs. Placebo; Pooled active vs. Placebo
CFB in Cogstate Detection Test score at Week 11 (Visit 5)	Secondary	ANCOVA	Higher dose vs. Placebo; Lower dose vs. Placebo; Pooled active vs. Placebo
CFB in Cogstate Identification Test score at Week 11 (Visit 5)	Secondary	ANCOVA	Higher dose vs. Placebo; Lower dose vs. Placebo; Pooled active vs. Placebo
CFB in Cogstate One Back Test score at Week 11 (Visit 5)	Secondary	ANCOVA	Higher dose vs. Placebo; Lower dose vs. Placebo; Pooled active vs. Placebo
CFB in MDHI total Score at Week 11 (Visit 5)	Secondary	MMRM	Higher dose vs. Placebo; Lower dose vs. Placebo; Pooled active vs. Placebo
CFB in CGI-S score at Week 11 (Visit 5)	Secondary	MMRM	Higher dose vs. Placebo; Lower dose vs. Placebo; Pooled active vs. Placebo
CFB in PGI-S score at Week 11 (Visit 5)	Secondary	MMRM	Higher dose vs. Placebo; Lower dose vs. Placebo; Pooled active vs. Placebo
CFB in SART go score at Week 11 (Visit 5)	Secondary	Kruskal-Wallis	Higher dose vs. Placebo; Lower dose vs. Placebo; Pooled active vs. Placebo
CFB in SART no-go score at Week 11 (Visit 5)	Secondary	Kruskal-Wallis	Higher dose vs. Placebo; Lower dose vs. Placebo; Pooled active vs. Placebo
CFB in SART total score at Week 11 (Visit 5)	Secondary	Kruskal-Wallis	Higher dose vs. Placebo; Lower dose vs. Placebo; Pooled active vs. Placebo

Endpoint	Primary/ Secondary/ Exploratory	Inference model	Comparisons of interest
CFB in MSL at Week 11 (Visit 5)	Exploratory	ANCOVA	Higher dose vs. Placebo; Lower dose vs. Placebo; Pooled active vs. Placebo

Abbreviations: ANCOVA = Analysis of Covariance; CGI-S = Clinical Global Impression of Severity; CFB = Change from Baseline; DSS = Daytime Sleepiness Scale; ESS = Epworth Sleepiness Scale; FSS = Fatigue Severity Scale; MDHI = Myotonic Dystrophy Health Index; MSL = Mean Sleep Latency; PGI-S = Patient Global Impression of Severity.

## 11.4.2 Primary Efficacy Analysis

### 11.4.2.1.1 Daytime Sleepiness Scale (DSS)

The DSS is a questionnaire in which patients are asked to assess five items with scores of never (0), seldom (1), often (2), and always (3). The DSS score is the sum of the answers to questions 1 to 4 plus the reversed score to question 5 (i.e., minus the score for question 5). If at least one question is not answered, the score will be set to missing.

The DSS score can vary from 0 to 15 and the higher the score, the higher the degree of sleepiness. The questionnaire was developed and validated in patients with DM1 in three subgroups: early adult-onset (onset of symptoms from 11-20 years old), adult (onset of symptoms from 21-40 years old) and mild (onset of symptoms at >40 years old). The instrument has demonstrated construct (factorial) validity ([Laberge et al 2004](#)), convergent and discriminant validity ([Laberge et al 2009](#); [Laberge and Dauvilliers 2010](#)) and responsiveness ([Laberge et al 2021](#)).

A descriptive summary of DSS (mean, SD, median, minimum, maximum) for the absolute values and change from Baseline to Week 7 and to Week 11 will be presented by treatment group and for the active groups combined. If the termination visit occurs after the Week 7 Double-Blind visit, the early termination data will be windowed to Week 11 regardless of the discontinuation reason.

The change from Baseline to Week 11 will be analyzed using a Mixed Model Repeated Measures (MMRM) approach. Fixed effects will be included for treatment, visit, treatment\*visit interaction, baseline value, and stratification factor. An unstructured covariance structure will be utilized; in case of failure to converge, covariance structures TOEPH (Heterogeneous Toeplitz), ARH(1) (Heterogeneous auto-regressive 1), and VC (Variance Components) will be tested in the order specified. Least Square means, standard errors, and the LS mean differences (each treatment versus placebo and the pooled active groups versus placebo) at each visit will be reported. All estimates will be generated from a single model, i.e., the pooled active estimates will be created via model contrasts.

If there is more than a 10% difference between the stratification factor recorded in IRT versus the stratification factor derived from the prior and concomitant in the EDC, the MMRM analysis will be repeated using the stratification factor reported in IRT.

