## 6.2.1. Daytime Sleepiness Scale

The DSS is a questionnaire in which patients are asked to assess five items with scores of never (0), seldom (1), often (2), and always (3), one of which is scored in the reverse order. The DSS score can vary from 0 to 15 and the higher the score, the higher the degree of sleepiness. It was developed and validated in patients with DM1 in three sub-groups: early adult-onset (onset of symptoms from 11-20 years old), adult (onset of symptoms from 21-40 years old) and mild (onset of symptoms at >40 years old). The instrument has demonstrated construct (factorial) validity (Laberge et al 2004), convergent and discriminant validity (Laberge et al 2009; Laberge and Dauvilliers 2010) and responsiveness (Laberge et al 2022). The DSS is provided in Appendix F.

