## APPENDIX F. DAYTIME SLEEPINESS SCALE (DSS)

### DAYTIME SLEEPINESS SCALE

For each statement, circle the number that best corresponds to what you are currently experiencing.

		Never or almost never	Sometimes	Often	Always or almost always
1.	I take one or more naps during the day.	0	1	2	3
2.	I occasionally have a sudden urge to sleep during the day.	0	1	2	3
3.	I occasionally fall asleep in front of the television or at the movies.	0	1	2	3
4.	I have difficulty remaining still for long periods of time.	0	1	2	3
		Always or almost always	Often	Sometimes	Never or almost never
5.	I am generally in great shape during the day.	0	1	2	3

Please note that question #5 is scored in the reverse order.

Total Score: \_\_\_\_\_

Daytime Sleepiness Scale Version date 12Nov2021

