## 6 Introduction

This SAP should be read in conjunction with the study protocol Amendment 5 dated 18 July 2023 and electronic case report form (eCRF) v4.0 dated 09May2023. Any changes to the protocol or eCRF may necessitate updates to the SAP.

The SAP Version 1 was approved on 28 April 2021. This SAP Amendment 1 (Version 2.0) will include changes to the protocol through protocol Amendment 5. Final approval of the SAP by Harmony Biosciences, LLC and ICON will occur prior to the database entry lock and unblinding of the database for the analyses of the Double-Blind Treatment Phase of the study.

If the statistical analyses described in the final SAP and final protocol differ, the statistical analyses in the SAP will be used for the analyses presented in the clinical study report (CSR). Substantive changes from the analyses specified in the protocol will be described in the SAP and in the CSR.

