### 11.4.4 Open-Label Extension Efficacy Analyses

The OLE efficacy parameters are:

- DSS
- ESS
- FSS
- Cogstate (Detection Test, Identification Test, One Back Test)
- MDHI Total score and sub-scores of sleep, fatigue and cognitive impairment
- CGI-S for EDS
- PGI-S for EDS

Actual and change from Baseline results in the OLE Phase will be summarized by using descriptive statistics at each open-label visit. Results will be tabulated by total. In addition, shift tables from baseline to each of the OLE visits will be provided for DSS, ESS, CGI-S and PGI-S.

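### The SAP's scoring rule for DSS item 5 cannot produce the 0–15 range it states, and it reverses the item twice if the database holds the number circled on the form

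*SAP*

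**What the plan says.** SAP 11.4.2.1.1 describes the DSS as "five items with scores of never (0), seldom (1), often (2), and always (3"). It forms the total from "questions 1 to 4 plus the reversed score to question 5 (i.e., minus the score for question 5"), and then adds: "The DSS score can vary from 0 to 15 and the higher the score, the higher the degree of sleepiness".

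Protocol section 6.2.1 uses the same never-to-always key, says of the five items "one of which is scored in the reverse order", and gives the same 0–15 range. Protocol Appendix F reproduces the form. Patients circle a printed number. Item 5, a positively worded statement about being in good shape in the daytime, has its own column header running from Always=0 to Never=3. A note under the form reads: "Please note that question #5 is scored in the reverse order".

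The SAP is written against "electronic case report form (eCRF) v4.0 dated 09May2023". Neither document says how that eCRF stores item 5.

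**The concern.** The spelled-out arithmetic and the stated range sit in one section and cannot both hold. A programmer who follows the parenthesis literally will not reproduce the instrument's score.

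The worse possibility comes from Appendix F. The printed number for item 5 is already reversed, so it only has to be added. If the database holds the circled number, subtracting it turns an improvement on that item into an apparent worsening.

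Change in DSS is the sole primary endpoint. Protocol 9.1 and SAP section 6 both let the SAP prevail for the study report where the two differ. SAP 6.1 records that the sensitivity analyses were removed. The one planned repeat of the primary analysis, with the IRT stratification factor (SAP 11.4), would reuse the same DSS score and so could not expose the error.

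**Working it through.** **Inputs.** Five items scored 0–3 (SAP 11.4.2.1.1, Protocol 6.2.1); SAP rule Q1+Q2+Q3+Q4−Q5; stated range 0–15; item 5 printed Always=0, Often=1, Sometimes=2, Never=3 (Protocol Appendix F).

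Let S = Q1+Q2+Q3+Q4, which runs from 0 to 12. Let p be the number circled for item 5 and f = 3 − p the same answer on the never=0 to always=3 key. Both p and f run from 0 to 3.

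**1. Reproducing the stated range.** The sum of the five printed numbers is S + p, from 0 + 0 = 0 to 12 + 3 = 15. Equivalently, S + (3 − f) also runs from 0 to 15. The stated range is right for the instrument.

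**2. The SAP rule.** Subtracting item 5 gives 0 − 3 = −3 at the bottom and 12 − 0 = 12 at the top. This holds for either coding. Enumerating all 4^5 = 1024 response patterns confirms it.

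**3. Coding A: the circled number p is stored.** The SAP total is S − p = (S + p) − 2p. Each total is too low by twice the circled number: 0, 2, 4 or 6 points. For change from Baseline, SAP change = true change − 2 × (change in p).

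- All five items improve by 1: true change −5; SAP change −4 + 1 = −3.
- Only item 5 improves, by 1: true change −1; SAP change +1.
- If item 5 carries a share w of the true treatment effect, the SAP score keeps (1 − w) − w = 1 − 2w of it. The documents give no item-level effects, so w is an assumption: w = 0.1, 0.2 (even spread) and 0.3 give 80%, 60% and 40%.

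**4. Coding B: the frequency code f is stored.** The SAP total is S − f = S − (3 − p) = (S + p) − 3, a constant 3 points low. The constant cancels in change from Baseline. In the model it only shifts the baseline covariate, which the intercept absorbs. A numerical check in a baseline-adjusted linear model left the treatment coefficients identical.

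**5. The two extreme patients.**

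| Pattern | Correct total | SAP rule, coding A | SAP rule, coding B |
|---|---|---|---|
| Least sleepy: Never on items 1–4, Always on item 5 | 0 | 0 | −3 |
| Most sleepy: Always on items 1–4, Never on item 5 | 15 | 12 − 3 = 9 | 12 − 0 = 12 |

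**6. Would impossible totals reveal the error?** A negative total needs S below the stored value of item 5. The patterns with S = 0, 1 and 2 number 1, 4 and 10. Item 5 stored as 1, 2 or 3 therefore gives 1, 1 + 4 = 5 and 1 + 4 + 10 = 15 negative patterns, 21 of 1024 (2.1%). This counts patterns; it is not an expected frequency in patients. Under coding B these are patients with few complaints who feel in good shape, a coherent picture. Under coding A they are patients with few complaints who feel in poor shape, which is less coherent. A range check is thus weakest where the harm is greatest.

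**The case against.** The strongest reply is that the serious harm is not established. Only coding A distorts the primary estimate, and the eCRF that would settle the matter cannot be seen. The key written in the SAP is never=0 to always=3. If the data follow it, the sign of the subtraction is right and nothing is lost in change scores or contrasts. The word reversed, read with the 0–15 range, suggests that 3 minus the score was meant and that the parenthesis is a loose gloss. The mismatch in coding lies between the Appendix F layout and the text of both documents, since Protocol 6.2.1 uses the SAP's key. The study is also exploratory, and no formal test is planned on the DSS.

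Much of this stands. Double reversal is a conditional risk, and the 80/60/40% figures are illustrations. The planned open-label tables ("shift tables from baseline to each of the OLE visits will be provided for DSS, ESS, CGI-S and PGI-S") have no DSS cut-offs in either document, so misclassification cannot be shown. Under coding B a patient's raw shift is unchanged, and only the levels are 3 points low.

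The main point survives. No 0–3 coding makes the sentence correct as written. The charitable reading does not remove the risk either: if the circled number is stored, 3 minus that number still reverses item 5 twice, and every total then falls within 0–15, so a range check passes.

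**Conclusion.** The concern holds. The derivation of the primary score is wrong as written: it yields −3 to 12 against a stated 0 to 15, and this needs no assumption beyond the 0–3 item scores.

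The effect on results depends on the stored coding of item 5:

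- **Circled number stored:** the primary estimate and its baseline covariate are both distorted, and absolute totals are 0 to 6 points low. With an even spread of effect over the items (an assumption), 60% of the raw effect remains.
- **Frequency code stored:** change from Baseline and treatment differences are unaffected, and every absolute DSS summary is exactly 3 points low.

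Because the DSS analysis is descriptive (Protocol 9.1.2, SAP section 11), the risk is a misleading estimate or table and not a wrong test decision. In a trial of about 30 patients whose main product is that estimate, the rule should be corrected before unblinding.

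**What to change.** 1. Look up how eCRF v4.0 and the database store item 5.
2. Replace the parenthesis in SAP 11.4.2.1.1 with an explicit rule, for example:

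> DSS total = Q1 + Q2 + Q3 + Q4 + Q5, with item 5 coded as printed on the form (Always=0 to Never=3). If item 5 is stored as Never=0 to Always=3, use 3 minus the stored value. Range 0–15.

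3. Program a check that every total lies in 0–15, and add one test record: Always on items 1–4 and Never on item 5 must total 15. The current rule gives 9 or 12, and 3 minus an already reversed item gives 12, so this record catches all three errors where a range check would not. The total line on the paper form is a further cross-check where it has been filled in.

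The cost is one look-up, one SAP sentence, one program line and one test record. SAP section 6 places final approval before database lock and unblinding, which is the time to do it. If outputs already exist, the same look-up shows whether they need correction.

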## 11.4.3 Secondary Efficacy Analyses

Descriptive summary (mean, SD, median, minimum, maximum) of each of the secondary endpoints will be provided for absolute values and for change from baseline. All summaries will be presented by treatment group and for the active groups combined.

### 11.4.3.1.1 Fatigue Severity Scale (FSS)

The FSS is a 9 item patient reported outcome assessment that covers physical, social, and cognitive effects of fatigue such as function, work, and motivation ([Krupp et al 1989](#) and [Hewlett et al 2011](#)). The 9 items are summed and then averaged (i.e., divided by 9) to produce a global score. Each item has seven choices from strongly disagree to strongly agree (1-7), and the recall period is the past week. The higher the score, the more severe the fatigue is and the more it affects the person's activities.

If the number of missing items is <4, the FSS total score is derived as the mean of the non-missing items; if 4 or more items are missing, the total score is set to missing ([Rosa 2014](#)).

Early termination visits will be summarized and analyzed under Week 7 or Week 11 (depending on which visit they are closest to, see [section 9.2](#) on visit window) regardless of the discontinuation reason.

A descriptive summary of the FSS absolute values and change from Baseline to Week 7 and to Week 11 will be reported by treatment group and for the active groups combined.

---

The change from Baseline will be analyzed using a Mixed Model Repeated Measures (MMRM) approach. Fixed effects will be included for treatment, visit, treatment\*visit interaction, baseline value, and wake-promoting agents stratification factor. An unstructured covariance structure will be utilized; in case of failure to converge, covariance structures TOEPH (Heterogeneous Toeplitz), ARH(1) (Heterogeneous autoregressive 1), and VC (Variance Components) will be tested in the order specified. Least Square means, standard errors, and the LS mean differences (each treatment versus placebo and the pooled active groups versus placebo) at each visit will be reported. All estimates will be generated from a single model, i.e., the pooled active estimates will be created via model contrasts.

#### 11.4.3.1.2 Cogstate Detection Test

The Cogstate detection test is a computerized measure of psychomotor function and uses a validated simple reaction time (890-) paradigm with playing card-like stimuli displayed on a computer screen. In this test, the playing cards all depict the same image. The patient is asked to press the “yes” key as soon as the card in the center of the screen turns face up. The software measures the speed and accuracy of each response. The main outcome measure for the test is speed of performance (mean of the log10-transformed RTs for correct responses). Decreasing scores represent improved test performance.

Early termination visits will be summarized and analyzed under Week 11 (see [section 9.2](#) for details on the visit window) regardless of the discontinuation reason.

A descriptive summary of Cogstate detection test for the absolute values and change from Baseline to Week 11 will be reported by treatment group and for the active groups combined.

In addition, similarly to the primary endpoint (see [section 11.4.2.1.1](#)) but without the multiple imputations, the change from Baseline will be analyzed with an ANCOVA. Fixed effects will be included for treatment, Baseline value, and stratification factor. LS means, SEs, and the LS mean differences (each treatment versus placebo and the pooled active groups versus placebo) will be reported. All estimates will be generated from a single model, i.e., the pooled active estimates will be created via model contrasts. The effect size (magnitude of the differences between treatment groups and placebo) will also be provided.

The analysis of the Detection Test will be performed by Cogstate; more details are provided in the Cogstate SAP.

